7.2.3 Standard-of-Care Procedures

The following procedures will be performed at intervals determined by the SOC at each investigational site (refer to Appendix 1, Schedule of Events Table):

- Laboratory evaluations including:
 - hematology complete blood count
 - chemistry basic metabolic panel and electrolytes
- Diagnosis of neonatal morbidities including bronchopulmonary dysplasia (BPD), retinopathy of prematurity (ROP), intraventricular hemorrhage (IVH), periventricular leukomalacia (PVL), necrotizing enterocolitis (NEC), and late-onset sepsis in enrolled premature infants born at 24 to <37 weeks of gestation up to 1 month CA with a birth weight ≥750g.

7.2.4 Days 15, 30, 45, 60, 75 and 90 or End of Study Treatment Procedures

The Study Treatment Period starts when the patient receives study treatment. End of study treatment is defined as the last day of PN with Intralipid or Clinolipid; maximum 90 days of study treatment is allowed.

The following procedures will be performed approximately every 15 days ± 2 days for patients continuing on PN (days 15, 30, 45, 60, 75 and 90) and within ± 2 days of the last day of study treatment (maximum 90 days on either Clinolipid or Intralipid) whenever that occurs:

- Physical examination including weight, length or height (and head circumference for infants <1 year of age)
- Vital signs
- Concomitant medications
- Concomitant procedures
- AEs
- Laboratory evaluations including:
 - Hematology parameters
 - Serum chemistry parameters
 - Hepatic integrity parameters
 - Total and direct bilirubin
 - Triglyceride levels
 - FA profile
 - Holman Index
 - Phytosterol, cholesterol, and squalene levels

In addition, the following data will be collected at end of study treatment:

 Diagnosis of neonatal morbidities including bronchopulmonary dysplasia (BPD), retinopathy of prematurity (ROP), intraventricular hemorrhage (IVH), periventricular leukomalacia (PVL), necrotizing enterocolitis (NEC), and lateonset sepsis in enrolled premature infants born <37 weeks of gestation up to 1 month CA.

After end of study treatment (maximum of 90 days), the patient will receive nutritional intervention as prescribed by their healthcare provider as SOC if PN is still required.

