1.4 Study Design

1.4.1 Overall Study Design and Plan

This is a multi-center, randomized, double-blind, controlled, safety and efficacy study to evaluate the occurrence of EFAD (diagnosed by Holman Index >0.4) in pediatric patients receiving either Clinolipid or standard-of-care soybean oil-based ILE (Intralipid) in the hospital setting from 7 up to 90 days as part of PN. The risk of developing liver disease, including PNALD (defined by direct bilirubin $\geq 2 \text{ mg/dL}$) when no other etiology for liver dysfunction is present, also will be assessed.

Approximately 100 pediatric patients, including neonates, will participate in the study. Patients will be randomized in a 1:1 ratio to the treatment groups (Clinolipid or Intralipid) according to a central dynamic randomization scheme stratified by site and age group (premature infants born <37 weeks of gestation, full-term neonates born \geq 37 weeks of gestation to <1 month of age, infants 1 to <12 months of age, children 1 to <10 years of age, adolescent 10 to <18 years of age). In the case of multiple birth pregnancies, the infants will be assigned to the same treatment group.

Holman Index and FA profile will be evaluated. Select polymorphisms in the FA desaturase genes FADS1 and FADS2, will be determined in a subset of patients. The major plasma phytosterols found in the ILEs (stigmasterol, campesterol, sitosterol), cholesterol, and squalene will also be assessed.

The study consists of a Screening Period to confirm the patient's eligibility for the study after the informed consent form (ICF) and assent (if applicable) is signed and a Treatment Period, where study Day 1 is defined as the first day the patient receives study treatment.

End of study treatment is defined as the last day of PN with Intralipid or Clinolipid; maximum 90 days of study treatment is allowed.

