1.4.2 Determination of Sample Size

The sample size of 100 patients (50 in each of the 2 treatment groups: Clinolipid vs Intralipid), including neonates, is based on the feasibility of timely enrollment of patients for generating reference data and summary descriptive statistics, rather than on a formal power calculation. No formal hypothesis testing is planned.

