2.4.1.1 Derivation of Primary Endpoint

The primary endpoint is the incidence of EFAD which is defined in the protocol and will be derived based on the Holman Index (Triene/Tetraene Ratio) provided by the central laboratory.

- Holman Index <0.2: normal EFA
- Holman Index 0.2 0.4: at risk for EFAD
- Holman Index >0.4: EFAD

A patient will be considered 'at risk for developing EFAD' if they have a Holman Index of 0.2 - 0.4 at any timepoint during the study treatment.

A patient will be considered as an incident of EFAD (the 'event') if they have a Holman Index >0.4 at any timepoint during the study treatment.

For time to EFAD Kaplan Meier analyses, the index time will be the start of treatment. The first incident of EFAD will be considered the event and will use the date of EFAD (date first lab with Holman Index >0.4 reported). Patients will be censored if they do not develop EFAD during their follow-up or if they die before developing EFAD at the time of their last Holman Index laboratory measurement. Time to EFAD will be calculated for each patient who develops EFAD as follows and standardized to days:

The incidence rate of EFAD (events per 100 patient days) will be calculated as the following per treatment group:

```
Number of patients developing EFAD * 100
Total patient days
```

The total number of patient days will be calculated per treatment group as follows:

$$\sum_{i=1}^{n} (Date of First EFAD Occurrence or End Date of Treatment)$$

- Start Date of Treatment)_i + 1

Where n is the total number of patients per treatment group. If a patient develops EFAD, then the date of first EFAD occurrence will be used, and if they do not, then end date of treatment will be used. If more than one instance of EFAD occurs, the patient will be counted once and the date of first occurrence will be used. This will then be standardized to days.

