2.4.1.2 Analysis of Primary Endpoint

Holman index scores will be summarized descriptively by timepoint per treatment group using n, mean, standard deviation, minimum, Q1, median, Q3, and maximum.

The frequency and percentage of patients at risk of developing EFAD (Holman Index 0.2-0.4) as well as those who developed EFAD (Holman Index >0.4) will be summarized by timepoint and at the maximum by treatment group. The denominator for the percentage of patients will be the number of patients in the population who had at least one post-baseline Holman Index measurement available. The incidence rate (per 100 patient days) of EFAD will also be calculated per treatment group.

If there are more than 5 cases of EFAD per arm, then time to develop EFAD will be analyzed using survival analysis approach (cumulative incidence), and the mean, standard error, Q1, median, Q3, minimum, and maximum for each treatment group will be displayed, where calculable. A cumulative incidence plot will also be produced. If there are less than 5 cases of EFAD in each treatment arm, then time to developing EFAD will be summarized descriptively by treatment group using n, mean, standard deviation, minimum, Q1, median, Q3, and maximum. If no events occur, then time to EFAD will not be calculated.

A spaghetti plot consisting of Holman index values over time will be produced with one line representing each patient, and different types of lines or symbols (e.g. solid and dashed) representing each treatment group. Two bolded lines will be added at y=0.2 and y=0.4 to represent the bounds for being at risk of EFAD and developing EFAD.

As a supportive analysis to the primary endpoint, the following will be analyzed:

• FA profiles will be summarized using descriptive statistics (number of patients, mean, standard deviation, median, minimum, and maximum) in each of the 2 treatment groups (Clinolipid vs Intralipid), as well as descriptive statistics of genetic polymorphisms in the FADS1 and FADS2 genes for the patients with buccal swabs with the 5 highest and 5 lowest arachidonic acid values in each treatment group.

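### The survival-analysis mean and SE for time to EFAD and PNALD have no common restriction time, so when they are displayed they may not be comparable between arms and can favour the arm with more events.

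*SAP*

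**What the plan says.** SAP 2.4.1.2 applies when there are more than 5 EFAD cases per arm. It calls for a survival (cumulative incidence) analysis of time to EFAD, "and the mean, standard error, Q1, median, Q3, minimum, and maximum for each treatment group will be displayed, where calculable". SAP 2.4.2.2.2 uses the same list for PNALD under the same trigger. Neither section gives a restriction time or calls the mean restricted.

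On censoring, SAP 2.4.1.1 states: "Patients will be censored if they do not develop EFAD during their follow-up or if they die before developing EFAD"; the censoring time is the last Holman Index measurement. SAP 2.4.2.2.1 censors PNALD at the last laboratory value.

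Follow-up varies by patient. SAP 1.4.1 describes treatment "in the hospital setting from 7 up to 90 days as part of PN", and Protocol 7.2.4 adds: "End of study treatment is defined as the last day of PN with Intralipid or Clinolipid; maximum 90 days of study treatment is allowed". Sampling is on a coarse grid: "The following procedures will be performed approximately every 15 days ± 2 days for patients continuing on PN", with a further sample at end of treatment.

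The sample size "is based on the feasibility of timely enrollment of patients", and SAP 1.4.2 states: "No formal hypothesis testing is planned".

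**The concern.** A Kaplan-Meier mean is the area under the whole curve. It can be estimated without a cut-off only if the curve reaches zero, which happens only when whoever remains under observation at the longest follow-up time has the event. With censoring between about 7 and 90 days and a minority of patients having the event, the curve will usually stop above zero. A program can then either report the mean as not estimable or print an area up to some cut-off. The proviso at the end of the SAP's list does not choose between these, because a truncated area can always be calculated.

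If the cut-off belongs to each arm separately, the two means are different quantities. An arm whose few events all come early gets a short area. An arm with the same early events plus a late one gets a much longer area, which looks like a longer time to deficiency. The SE has the same fault, since it measures the precision of a different quantity in each arm. In a study whose results are descriptive, the displayed table is the result, so a reversed or non-comparable pair of means matters even without a test.

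**Working it through.** The plan gives no figure to reproduce: there is no assumed event rate, PN duration or power.

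**Inputs from the documents.** 50 per arm (SAP 1.4.2); treatment 7 to 90 days (SAP 1.4.1); samples about every 15 days plus end of treatment (Protocol 7.2.4); trigger of more than 5 cases per arm (SAP 2.4.1.2, 2.4.2.2.2).

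**Assumed.** In both arms, last samples at Days 15/30/45/60/75/90 for 24/12/6/4/2/2 patients. Numbers at risk on those days are then 50/26/14/8/4/2.

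**Formulas.** Mean to cut-off τ = area under S(t) from 0 to τ. SE = √Σ[Aᵢ² dᵢ/(nᵢ(nᵢ − dᵢ))], where Aᵢ is the area from event time i to τ, dᵢ the events and nᵢ the number at risk.

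**Example 1.** Arm A has 6 events, all at Day 15, so S = 44/50 = 0.88 afterwards. Arm B has the same 6 plus one at Day 60, so S = 0.88 × 7/8 = 0.77 after Day 60. B can only be worse.

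- *Cut-off at each arm's last event.* A: 15.0, SE 0 because no area lies beyond Day 15. B: 15 + 0.88 × 45 = 54.6, SE = 39.6 × √(6/(50 × 44)) = 2.07. B looks about 40 days better. A's mean would still be 15.0 with 26 events at Day 15, because S = 1 up to that day.
- *Common Day 90.* A: 15 + 0.88 × 75 = 81.0. B: 54.6 + 0.77 × 30 = 77.7. The order is right. In this example both arms' last observation is also Day 90, so that cut-off gives the same answer.

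**Example 2.** A as before. B has 12 events (9 at Day 15, 2 at Day 30, 1 at Day 60): S = 0.82, then 0.82 × 24/26 = 0.757.

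- *Cut-off at last event.* A 15.0; B 15 + 0.82 × 15 + 0.757 × 30 = 50.0. Reversed.
- *Common Day 60.* 54.6 against 50.0. *Common Day 30.* 15 + 0.88 × 15 = 28.2 against 15 + 0.82 × 15 = 27.3. Right order both times.

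The median is not reached in any of these arms.

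**Chance of meeting the trigger.** P(at least 6 events of 50) is 4%, 38%, 78% and 95% at event risks of 5%, 10%, 15% and 20%. For both arms at equal risk, squaring gives about 0.1%, 15%, 61% and 91%.

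**Simulation under assumed rates.** 600 trials per row; PN = 7 days plus an exponential, capped at 90; samples every 15 days plus end of treatment. The last three columns give the share of trials meeting the trigger in which the arm with the higher hazard shows the longer mean. The common cut-off is the shorter of the two arms' longest follow-up.

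| 15-day risk, better arm | Hazard ratio | Mean PN before cap (days) | Trigger met | Own last event | Own last observation | Common cut-off |
|---|---|---|---|---|---|---|
| 10% | 2 | 20 | 361/600 | 40% | 25% | 13% |
| 10% | 2 | 30 | 534/600 | 34% | 8% | 6% |
| 10% | 2 | 45 | 594/600 | 22% | 3% | 3% |
| 15% | 2 | 20 | 562/600 | 36% | 14% | 5% |
| 15% | 2 | 30 | 598/600 | 23% | 6% | 4% |
| 15% | 2 | 45 | 600/600 | 8% | 1% | 1% |
| 15% | 1.5 | 20 | 552/600 | 41% | 31% | 20% |
| 15% | 1.5 | 30 | 596/600 | 38% | 17% | 16% |
| 15% | 1.5 | 45 | 600/600 | 22% | 11% | 10% |

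In 92% to 100% of these trials the curve stayed above zero in at least one arm.

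**The case against.** The strongest objection is that the SAP never says the mean stops at each arm's last event. A reader might infer it from usual software behaviour, but the SAP names only the software, and a programmer could properly show the mean as not calculable. This stands: the own-last-event figures describe one way of carrying out the plan. Stopping at each arm's last observation misranks less often. For mean PN of 30 days or more it does about as well as a common cut-off.

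Other stronger readings also go beyond the documents:

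- **That a mean exists only if every patient is followed to the event.** A product-limit curve reaches zero whenever the longest-followed patient has the event, however many others are censored.
- **That this is the headline result.** SAP 1.6.1 lists time to EFAD as supportive. The number and percentage with EFAD, the rate per 100 patient-days and a cumulative incidence plot are also planned.
- **That follow-up differs between arms.** The documents show only that it differs between patients. The reversal does not need a between-arm difference.
- **That the table will appear.** It needs more than 5 cases per arm. With assumed hazards of 0.6 against 0.2 per 100 patient-days, the trigger was met in only about 0.1% to 5% of simulated trials.

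The Day 15 example is also extreme, since visits have a ±2-day window and end-of-treatment samples fall on other days. A common cut-off does not remove misranking either, so part of it is small-sample noise.

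One alternative reading does not rescue the plan. SAP 2.4.1.1 computes time to EFAD for patients who develop it. A cases-only mean in Example 1 is 15.0 for A and (6 × 15 + 60)/7 = 21.4 for B, so the worse arm still looks better.

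**Conclusion.** The point holds in a limited form. When the trigger is met, the SAP displays a survival mean and SE per arm without defining what they estimate. In most realistic data the unrestricted mean is not estimable. If an arm-specific cut-off is used, the two arms' figures are not comparable, and the arm with more EFAD or PNALD can show the longer mean.

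That reversal is arithmetic. Its frequency is not known. At an assumed hazard ratio of 2, and given the trigger, the table shows 8% to 40% with each arm's last event as cut-off, 1% to 25% with its last observation, and 1% to 13% with a common cut-off. These ranges rest on assumed event rates and PN durations that the documents do not give. The harm is a misleading entry in a supportive, untested table. No test or decision rule depends on it. It is still worth correcting, because the numbers can mislead when the plan is followed as written.

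**What to change.** In SAP 2.4.1.2 and 2.4.2.2.2, drop the unrestricted mean and SE. Report per arm the Kaplan-Meier cumulative probability of EFAD and of PNALD at Days 15, 30, 45, 60, 75 and 90, where estimable, with 95% CI and number at risk. In Example 1 this would show 12% in both arms up to Day 45, then 12% against 1 − 0.77 = 23% at Day 60 with 8 at risk, which puts the arms in the right order and shows how little late data there are.

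If a mean is kept, label it as restricted and use one horizon for both arms, fixed in the SAP before unblinding. Quartiles, minimum and maximum may stay.

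The cost is SAP wording and the table shells, with no new data. The drawback is that late-day estimates will have wide intervals or be shown as not estimable.

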9.5 Primary Endpoint

The primary endpoint is the risk of developing EFAD defined as defined by Figure in Appendix 3.

- The risk of developing EFAD in pediatric patients will be summarized by treatment group as frequency and percentage. Time to developing EFAD will be analyzed using the Kaplan-Meier approach.
- Both incidence rate and proportion of EFAD will be computed for each treatment group.
- The incidence rate of EFAD will be computed as the number of patients who develop EFAD during the Study Treatment Period divided by the corresponding person time (i.e. "person-day" which is computed as "total number of patients" times "treatment exposure period [day]" in the corresponding treatment group), and reported as per 100 patient days.
- The proportion of EFAD will be computed as the number of patients who develop EFAD during the Study Treatment Period divided by the corresponding total number of patients.

- The Holman Index will be summarized with descriptive statistics (number of patients, mean, standard deviation, median, minimum, and maximum) on an approximately 15-day basis in each of the 2 treatment groups (Clinolipid vs Intralipid).
- FA profiles will be summarized using descriptive statistics (number of patients, mean, standard deviation, median, minimum, and maximum) in each of the 2 treatment groups (Clinolipid vs Intralipid), as well as descriptive statistics of genetic polymorphisms in the FADS1 and FADS2 genes.

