1.6 Endpoints

1.6.1 Primary Endpoint

• Risk of EFAD. EFAD will be defined using the Holman Index value of >0.4.

Supportive of the primary endpoint

- Time to developing EFAD
- The Holman Index
- Fatty acid (FA) profiles
- Genetic polymorphisms in FADS1 and FADS2 genes

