3. CHANGES FROM ANALYSIS PLANNED IN PROTOCOL

There are no planned changes in analyses from the protocol.

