16.2.11.1.2	FAS	Parenteral Nutrition Macronutrients
16.2.11.2.1	FAS	Enteral Nutrition Intake: Formula, Breast
		Milk, and Nutritional Shakes
16.2.11.2.2	FAS	Enteral Nutrition Intake: Additives and
		Fortifiers
16.2.11.2.3	FAS	Enteral Nutrition Intake: Oral Intake /
		Breastfeeding
16.2.11.2.4	FAS	Enteral Nutrition Macronutrients
16.2.11.3.1	FAS	IV Fluid Intake in addition to Parenteral
		Nutrition
16.2.11.3.2	FAS	IV Fluid Intake Macronutrients
16.2.11.4.1	FAS	Overall Nutritional Intake

Figure Number	Analysis	Figure Name
	Population	
14.2.1	FAS	Box Plots of Growth Parameters by
		Treatment Group
14.3.5.2.1	FAS	Holman Index over Time
14.3.5.2.2	PPS	Holman Index over Time
14.3.6.1.1	FAS	Direct Bilirubin over Time
14.3.6.1.2	PPS	Direct Bilirubin over Time
14.3.6.2.1	FAS	Assessment of Drug Induced Liver Injury:
		ALT
14.3.6.2.2	FAS	Assessment of Drug Induced Liver Injury:
		AST
14.3.6.2.3	FAS	Time Course of Hy's Law Cases
14.3.6.3.2	FAS	Scatterplots of Plasma Phytosterols vs. Direct
		Bilirubin
14.3.6.4.1.1	FAS	Box Plots of Ordered Parenteral Nutrition
		Intake by Treatment Group
14.3.6.4.1.2	FAS	Box Plots of Administered Parenteral
		Nutrition Intake by Treatment Group
14.3.6.4.2.1	FAS	Box Plots of Ordered Enteral Nutrition Intake
		by Treatment Group
14.3.6.4.2.2	FAS	Box Plots of Administered Enteral Nutrition
		Intake by Treatment Group
14.3.6.4.3	FAS	Box Plots of Administered IV Fluid Intake by
		Treatment Group
14.3.6.4.4.1	FAS	Box Plots of Overall Ordered Nutritional
		Intake by Treatment Group
14.3.6.4.4.2	FAS	Box Plots of Overall Administered Nutritional
		Intake by Treatment Group

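### The SAP puts an undeclared case-count condition on the protocol's Kaplan-Meier analyses of time to EFAD and PNALD, and some case counts have no rule

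*SAP*

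**What the plan says.** Protocol 9.5 reads: "Time to developing EFAD will be analyzed using the Kaplan-Meier approach". The synopsis says the same, and Protocol 9.6.1.1 plans the same method for time to PNALD. None of these places sets a minimum number of cases.

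SAP 2.4.1.2 adds one: "If there are more than 5 cases of EFAD per arm, then time to develop EFAD will be analyzed using survival analysis approach", followed by "A cumulative incidence plot will also be produced". The alternative branch is: "If there are less than 5 cases of EFAD in each treatment arm, then time to developing EFAD will be summarized descriptively". With no events, nothing is calculated. SAP 2.4.2.2.2 repeats the scheme for PNALD and expressly limits the descriptive summary to patients who develop it. For EFAD the same limit follows from SAP 2.4.1.1: "Time to EFAD will be calculated for each patient who develops EFAD". That section also defines index time, event and censoring for Kaplan-Meier without any count condition.

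SAP 3 states: "There are no planned changes in analyses from the protocol". SAP 1.6.1 lists time to EFAD under "Supportive of the primary endpoint".

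The figure list in SAP Appendix 1 has no cumulative incidence plot for EFAD or PNALD. It does list "Time Course of Hy's Law Cases", which is also conditional on what the data show.

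SAP 2.4.1.2 uses one denominator, patients with any post-baseline Holman result, for EFAD percentages both by timepoint and at the maximum.

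**The concern.** There are three linked problems.

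- **Undeclared change of method.** At low counts the SAP replaces the protocol's estimator with a different quantity. A mean time among cases carries no information on risk and ignores everyone censored. What disappears is the cumulative risk by Day 15, Day 30 and so on, allowing for patients who have left. With treatment lasting 7 to 90 days, that can differ clearly from the simple proportion.
- **Incomplete rule.** The two conditions are not complementary. Where neither is met, the output would be chosen once the counts are known. Split counts are plausible, because the protocol's introduction puts Clinolipid at about one third of the linoleic acid content of a pure soybean oil emulsion.
- **Outputs that do not match the text.** The promised plots are not in the figure list.

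A lesser point concerns the percentages by timepoint. The SAP does not say whether they count patients above 0.4 at that visit or cumulatively. On the per-visit reading, patients who have left stay in the denominator and dilute the percentages at intermediate visits. The combined Day 90/end-of-treatment visit is less affected.

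**Working it through.** **Inputs.** 50 patients per arm (Protocol 9.2, SAP 1.4.2); the two conditions in SAP 2.4.1.2. There is no planned power or event count to reproduce, because the sample size rests on feasibility and no hypothesis is tested. The documents give no EFAD rate, so the risks below are assumed, with independent binomial counts.

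**Coverage, read literally.** Each arm can have 0 to 50 cases, giving 51 × 51 = 2601 pairs. Both above 5: 45 × 45 = 2025. Both below 5: 5 × 5 = 25. No rule: 2601 − 2025 − 25 = 551 (21%). The survival branch needs at least 6/50 = 12% observed in both arms.

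**Probabilities.** Let F(k; p) and f(k; p) be the binomial cumulative and point probabilities for n = 50, with pC for Clinolipid and pI for Intralipid.

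- Descriptive branch: F(4; pC) × F(4; pI).
- No event in either arm: f(0; pC) × f(0; pI).
- Survival branch, literal: [1 − F(5; pC)] × [1 − F(5; pI)]. No rule is 1 minus this and minus the descriptive branch.
- If either arm above 5 is enough: no rule is F(5; pC) × F(5; pI) − F(4; pC) × F(4; pI), that is, a larger count of exactly 5.
- Arm by arm: an arm has no rule when it has exactly 5, so some arm lacks one with probability 1 − [1 − f(5; pC)] × [1 − f(5; pI)].

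| Assumed risk, Clinolipid/Intralipid | 2%/1% | 5%/1% | 10%/2% | 20%/5% |
|---|---|---|---|---|
| Descriptive branch | 0.9966 | 0.8963 | 0.4298 | 0.0166 |
| of which no event at all | 0.2203 | 0.0466 | 0.0019 | 0.0000 |
| Case-only summary replaces a curve | 0.7763 | 0.8497 | 0.4279 | 0.0166 |
| Survival branch, literal | 0.0000 | 0.0000 | 0.0002 | 0.0360 |
| No rule, literal | 0.0034 | 0.1037 | 0.5700 | 0.9475 |
| No rule, either arm | 0.0029 | 0.0660 | 0.1860 | 0.0296 |
| Some arm exactly 5, arm by arm | 0.0029 | 0.0660 | 0.1872 | 0.0934 |

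Read arm by arm at 20%/5%, a Clinolipid curve would stand beside an Intralipid case-only summary with probability 0.9520 × 0.8964 = 0.853.

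With an assumed 40 evaluable per arm, the descriptive branch has probability 0.9988, 0.9519, 0.6283 and 0.0723. No rule is 0.0012, 0.0481, 0.3717 and 0.9161 read literally, and 0.0011, 0.0342, 0.1653 and 0.0868 on the either-arm reading.

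**What the fallback hides.** Take 3 cases at days 15, 30 and 30 among 50 patients.

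- Mean time among cases: (15 + 30 + 30)/3 = 25 days. Proportion: 3/50 = 6%.
- Kaplan-Meier risk by Day 30 with 25 at risk then: 1 − (49/50)(23/25) = 9.8%.
- With 10 at risk: 1 − (49/50)(8/10) = 21.6%.

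The numbers at risk are assumed.

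**Visit denominator, per-visit reading only.** A true 10% at a visit prints as 10% × 0.8 = 8% if 80% are sampled there, or 10% × 0.5 = 5% if half are (assumed fractions).

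**The case against.** The strongest reply is that little is lost and the gap has a default. Time to EFAD is supportive and nothing is tested. The proportion, the rate per 100 patient days, Holman statistics by visit and a patient-level plot appear at any count. Protocol 9.1 leaves detail to the SAP. Where SAP 2.4.1.2 is silent, Protocol 9.5 and the Kaplan-Meier definitions in SAP 2.4.1.1 are unconditional, and Appendix 1 lists time-to-EFAD tables without a condition. A fallback at low counts is also defensible: in the three-case example, 95% log-log intervals run from about 3% to 29% (25 at risk) and 7% to 58% (10 at risk). Patients leave because parenteral nutrition ends, so censoring may be informative.

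Much of this stands as a limit on severity. The case-only reading for EFAD is an inference, whereas for PNALD it is explicit. The largest no-rule figure holds only on the literal reading. The missing figure entries and the denominator would not justify action alone.

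The main point remains. Unconditional wording in one SAP section and a condition in another contradict each other; they do not supply a default. The tables do not say which analysis fills them. Replacing the estimator goes beyond adding detail. Wide intervals are a reason to print numbers at risk; the case-only mean has no better claim to precision and does not estimate risk. Informative censoring deserves a caveat, but dropping censored patients altogether does not address it.

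**Conclusion.** The concern holds and the SAP should be changed. The conditional rule departs from the protocol for both EFAD and PNALD, SAP 3 does not declare it, and an arm with exactly 5 cases exposes a gap on every reading (on the either-arm reading, only when 5 is the larger count). That much rests on the text alone.

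The size depends on assumed EFAD risks. A case-only summary replaces a curve in 78%, 85%, 43% and 2% of trials across the four scenarios. No rule applies in 0.3% to 95% read literally, 0.3% to 19% on the either-arm reading, and 0.3% to 19% arm by arm. PNALD follows the same rule, but no PNALD-specific rates were examined. The harm is confined to a supportive analysis in a descriptive study; the primary proportion and rate are unaffected. The visit-percentage point is minor and applies only on the per-visit reading; a reader could rebuild those figures from the tabulated Holman n.

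**What to change.** Delete the 5-case condition in SAP 2.4.1.2 and 2.4.2.2.2. Name the estimator (cumulative incidence as one minus Kaplan-Meier) and report it for both arms whenever at least one event occurs in the trial, with cumulative risk and numbers at risk at the scheduled days. Add the two plots to the Appendix 1 figure list.

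If a condition is kept, define the output for every combination of counts, including exactly 5 and split arms, and declare it in SAP 3.

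For EFAD percentages by timepoint, state whether the count is per visit or cumulative. If per visit, divide by patients with a Holman result at that visit. Keep the any-post-baseline denominator for the maximum.

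Confidence intervals are an optional addition. For an arm with no events, an exact two-sided 95% interval on 0/50 has upper limit 1 − 0.025^(1/50) = 7.1%.

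The cost is SAP wording and two routine figures. Estimates will be imprecise when events are few, and the report should state as a limitation that stopping parenteral nutrition may be informative censoring.
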